**Infection**

- All Infections
- Serious Infection
- Legionella Infection
- Diverticulitis
- Opportunistic Infection Excluding Oral Candidiasis and TB
- Oral Candidiasis
- Tuberculosisa
  - Active Tuberculosisa
  - Latent Tuberculosisa
- Parasitic Infections
- Reactivation of Hepatitis B
- Progressive Multifocal Leukoencephalopathy (PML)

**Malignancies**

- Malignancies
- Lymphoma
- Hepatosplenic T-Cell Lymphomas (HSTCL)
- Non-Melanoma Skin Cancer (NMSC)
- Melanoma
- Leukaemia
- Other Malignancies Except Lymphoma, HSTCL, Leukemia, NMSC, and Melanoma

**Immune Reactions**

- Allergic Reactions Including Angioedema, Anaphylaxis
- Lupus-Like Reactions and Systemic Lupus Erythematosus (SLE)
- Vasculitisa
  - Cutaneous Vasculitisa
  - Non-Cutaneous Vasculitisa
- Sarcoidosis
- Autoimmune Hepatitis

**Cardiovascular/Vascular**

- Myocardial Infarction
- Cerebrovascular Accident
- Congestive Heart Failure
- Pulmonary Embolism

**Respiratory**

Interstitial Lung Disease

**Gastrointestinal Events**

Intestinal Perforation

Pancreatitis

**Skin and Subcutaneous Tissue Disorders**

Steven's Johnson Syndrome

Erythema Multiforme

Worsening and New Onset of Psoriasis

**Nervous System Disorder**

Demyelinating Disorders Including Multiple Sclerosis, Guillain-Barré Syndrome, and Optic Neuritis and Others

Amyotrophic Lateral Sclerosis

Reversible Posterior Leukoencephalopathy Syndrome (RPLS)

**Hematologic Events**

Hematologic Disorders Including Pancytopenia

**Hepatic Events**

Liver Failure and Other Liver Events (Except Gallbladder-Related Events)

**Other**

Humira Administration-related Medication Errors

Injection Site Reactions

- a. An additional column will be included in the spreadsheet to indicate the subcategories: active or non-active tuberculosis, cutaneous or non-cutaneous vasculitis.

This list might be modified at time of analysis to comply with any future version.

**Adverse Events by System Organ Class and Preferred Term**

The number and percentage of subjects experiencing AEs will be tabulated according to the primary MedDRA SOC and PT for each treatment group. Subjects reporting more than one AE for a given PT will be counted only once for that term (most severe incident for the severity tables and most related incident for the relationship tables). Subjects reporting more than one type of AE within a SOC will be counted only once for that SOC. Subjects reporting more than one type of AE will be counted only once in the overall total.

The following AEs will be summarized using the conventions described above:

- AEs
- AEs rated at least possibly related to study drug by the investigator
- AEs by highest relationship
- AEs by maximum severity
- SAEs
- AEs leading to discontinuation of study drug
- AEs leading to death
- AEs of special interest

A listing of subject numbers associated with AEs by SOC and PT will be provided.

By-subject listings will be provided for AEs at least possibly related to study drug, severe AEs, SAEs, AEs leading to discontinuation, AEs leading to death, and AEs of special interest. In addition, SAEs with onset after informed consent but before the first dose of adalimumab was administered will be considered as pre-treatment SAEs and will be listed separately.

### **Adverse Events by Maximum Severity**

Adverse events will also be summarized by maximum severity. If a subject has an adverse event with unknown severity, then the subject will be counted in the severity category of "unknown," even if the subject has another occurrence of the same event with a severity present. The only exception is if the subject has another occurrence of the same adverse event with the most extreme severity – "Severe." In this case, the subject will be counted under the "Severe" category.

### **Adverse Events by Maximum Relationship**

Adverse events will also be summarized by maximum relationship to study, as assessed by the investigator. If a subject has an adverse event with unknown relationship, then the subject will be counted in the relationship category of "unknown," even if the subject has

another occurrence of the same event with a relationship present. The only exception is if the subject has another occurrence of the same adverse event with a relationship assessment of "Probably Related" or "Possibly Related." In this case, the subject will be counted under the "Probably Related" or "Possibly Related" category, respectively.

### **Adverse Event Rates per 100 Subject-Years of Study Drug Exposure**

The analysis of AEs per 100 subject-years will be presented for the AE overview, for AEs by SOC and PT, and for SAEs by SOC and PT.

The treatment-emergent AE rate per 100 subject-years of exposure to study drug (ADA) will be calculated. For this calculation, one year will be considered to be 365.25 days. The numerator of the rate will be the total number of AEs reported that a subject can be counted more than once overall. The denominator of the rates will be the total number of days exposed to study drug summed across all treated subjects divided by 365.25. The AE rate per 100 subject-years of exposure will be calculated as  $[(\text{numerator}/\text{denominator})]*100$ . The number of AEs reported (numerator), the total number of years of study drug exposure (denominator), and the AE rate per 100 subject-years will be presented overall.

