6.1.1 Definitions

6.1.1.1 Adverse Event

An adverse event (AE) is defined as any untoward medical occurrence in a patient or clinical investigation subject administered a pharmaceutical product and which does not necessarily have a causal relationship with this treatment. An adverse event can therefore be any unfavorable and unintended sign (including an abnormal laboratory finding), symptom, or disease temporally associated with the use of a medicinal (investigational) product, whether or not the event is considered causally related to the use of the product.

Such an event can result from use of the drug as stipulated in the protocol or labeling, as well as from accidental or intentional overdose, drug abuse, or drug withdrawal. Any worsening of a pre-existing condition or illness is considered an adverse event.

Worsening in severity of a reported adverse event should be reported as a new adverse event. Laboratory abnormalities and changes in vital signs are considered to be adverse events only if they result in discontinuation from the study, necessitate therapeutic medical intervention, (meets protocol specific criteria [refer to Section 6.3 regarding toxicity management]) and/or if the Investigator considers them to be adverse events.

An elective surgery/procedure scheduled to occur during a study will not be considered an adverse event if the surgery/procedure is being performed for a pre-existing condition and the surgery/procedure has been preplanned prior to study entry. However, if the pre-existing condition deteriorates unexpectedly during the study (e.g., surgery performed earlier than planned), then, the deterioration of the condition for which the elective surgery/procedure is being done will be considered an adverse event.

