6.1.2 Adverse Event Severity

The Investigator will use the following definitions to rate the severity of each adverse event:

Mild	The adverse event is transient and easily tolerated by the subject.
Moderate	The adverse event causes the subject discomfort and interrupts the subject's usual activities.
Severe	The adverse event causes considerable interference with the subject's usual activities and may be incapacitating or life-threatening.

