- Systemic CS dose at each study time point.
- Central retinal thickness (mean of both eyes) at each study time point by OCT machine.

Categorical variables will be summarized by counts and percentages at each visit. 95% confidence intervals for proportions will be provided. Data will be analyzed by Non Responder Imputation (NRI) and as observed. For as observed analyses, graphs will be generated for subjects with active vs. inactive uveitis at entry of Study M11-327 for:

- Proportion of subjects with no active lesions in both eyes at each study time point.
- Proportion of subjects at each study time point with a Grade  $\leq 0.5+$  in AC cells in both eyes on Slit Lamp Exam, according to SUN criteria.
- Proportion of subjects at each study time point with Grade  $\leq 0.5+$  in vitreous haze in both eyes on indirect ophthalmoscopy, according to NEI/SUN criteria.

- Proportion of subjects at each study time point in quiescence defined as no active lesions,  $AC \leq 0.5$  and  $VH \leq 0.5$ .
- Proportion of subjects with steroid-free quiescence at each study time point.
- OCT evidence of macular edema in at least one eye at each study time point.

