### **11.1 Treatment-Emergent Adverse Events**

Treatment-emergent adverse events (AEs) are defined as any event with an onset date that is on or after the first dose of adalimumab in Study M11-327 and no more than 70 days after the last dose of study drug administration.

If an incomplete onset date was collected for an AE, the event will be assumed to be treatment emergent unless there is other evidence that confirms that the event was not treatment emergent (e.g., the event end date was prior to the study drug start date). In case of increasing severity of an existing AE, the worsening will be considered as a new AE with a new onset date.

AE data will be summarized using primary MedDRA system organ classes (SOCs) and preferred terms (PTs) according to the most current implemented version of the MedDRA

coding dictionary. The SOCs will be presented in alphabetical order and the PTs will be presented in alphabetical order within each SOC. For AEs with an incidence rate  $\geq 5\%$  in the adalimumab group and SAEs, the PTs will also be presented in decreasing frequency.

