### **Adverse Event Overview**

The number and percentage of subjects experiencing treatment-emergent AEs will be summarized for the following AE categories.

- AEs
- AEs rated at least possibly related to study drug by the investigator (Probably Related or Possibly Related)
- Severe AEs
- SAEs
- SAEs rated at least possibly related to study drug by the investigator (Probably Related or Possibly Related)
- AEs leading to discontinuation of study drug
- AEs leading to death
- Uveitis-related AEs (see below)
- AEs of special interest (see below)

Uveitis-related AEs will be:

- Loss of transparency of the cornea
- Band keratopathy
- Synechiae
- Cataracts
- Glaucoma/increased intraocular pressure
- Vitreous hemorrhage
- Macular edema
- Retinal detachment
- Epiretinal membrane

- Vitreo-macular traction
- Retinal ischemia
- Vision loss
- Hypotony

The current list of AEs of special interest for treatment with adalimumab is:

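### The only exposure-adjusted AE measure counts records, so the plan gives no exposure-adjusted risk per subject and no confidence interval on any safety figure

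*SAP*

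**What the plan says.** **The rate.** In the SAP 11.1 subsection on rates per 100 subject-years, the numerator is a count of records: "The numerator of the rate will be the total number of AEs reported that a subject can be counted more than once overall". The denominator is pooled exposure: "The denominator of the rates will be the total number of days exposed to study drug summed across all treated subjects divided by 365.25". The rate is planned for the AE overview, for AEs by SOC and PT, and for SAEs by SOC and PT. Events, years and the rate are shown; no interval is mentioned.

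**What counts as an event.** SAP 11.1 states: "In case of increasing severity of an existing AE, the worsening will be considered as a new AE with a new onset date". This follows Protocol 8.1.5 and matches the collection rule in Protocol 6.1.1.1: "Worsening in severity of a reported adverse event should be reported as a new adverse event". Protocol 6.1.2 has three grades: mild, moderate and severe.

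**Subject counts.** These are also planned. For the overview: "The number and percentage of subjects experiencing treatment-emergent AEs will be summarized for the following AE categories". For the SOC/PT tables: "The number and percentage of subjects experiencing AEs will be tabulated according to the primary MedDRA SOC and PT for each treatment group". Each subject counts once per PT, once per SOC and once in total. The subgroup overviews show n (%) next to E/100PY.

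**Intervals.** SAP 10.2 plans 95% intervals for efficacy means and also says "95% confidence intervals for proportions will be provided". SAP 11 plans none.

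**Follow-up.** Under Protocol 5.1 and 5.4.1, subjects leave at the next scheduled visit after local approval or reimbursement and are classed as completers. Others may stay until March 2018.

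**The concern.** A long-term safety study should be able to say what share of patients meets a given problem per year of treatment, and how precisely that is known. The two planned summaries each give part of this.

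- E/100PY adjusts for exposure, but it mixes first occurrences, recurrences and severity steps within one illness.
- The subject percentage counts people, but it treats someone who left at an early national approval like someone followed for years.

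The missing interval matters most for the rare events of special interest in SAP 11.1, such as lymphoma, PML and demyelinating disorders. There the count may be zero or one, and the useful statement is the upper limit that the data allow. Efficacy, which is secondary to safety here, does get intervals.

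**Working it through.** The documents state no AE rate, expected event count or precision target, so there is no figure to reproduce. The SAP formula is rate = events / (exposure days / 365.25) × 100. The planned 400 subjects come from the Protocol synopsis. Exposure, event counts and hazards below are assumptions for illustration.

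**1. Records per illness.** Let m be the share of illnesses that worsen once and s the share that worsen twice. Mean records per illness = 1 + m + 2s. With three grades, upward steps alone give at most 3 (m = 0, s = 1). Neither m nor s is in the documents, so the formula gives a mechanism and a ceiling but no estimate.

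**2. E/100PY does not identify how many people are affected.** Take 400 subjects followed 2 years each (800 subject-years) and 40 events: 40/800 × 100 = 5.0 E/100PY in every row. Suppose each affected subject gives up 1 year of risk time after the first event, so the first-event rate is k/(800 − k) × 100.

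| Subjects affected (k) | E/100PY | n (%) | First event per 100 subject-years |
|---|---|---|---|
| 40 | 5.0 | 10.0% | 40/760 = 5.26 |
| 20 | 5.0 | 5.0% | 20/780 = 2.56 |
| 10 | 5.0 | 2.5% | 10/790 = 1.27 |

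The planned n (%) separates these rows, but only because follow-up is equal in this example.

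**3. The percentage moves with follow-up.** At a constant first-event rate of 2 per 100 subject-years, the percentage affected is 100 × (1 − exp(−0.02T)). This gives 1.0% at T = 0.5 years, 2.0% at 1 year, 3.9% at 2 years and 7.7% at 4 years. The underlying risk is the same throughout.

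**4. Precision for rare events.** The exact two-sided 95% Poisson limits for x events are chi-square(0.025; 2x)/2 and chi-square(0.975; 2x + 2)/2, divided by subject-years and multiplied by 100. For x = 0 the upper limit is 3.689 events.

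| Assumed mean exposure | Subject-years | Upper limit, 0 events |
|---|---|---|
| 1 year | 400 | 0.92 per 100 |
| 2 years | 800 | 0.46 per 100 |
| 3 years | 1200 | 0.31 per 100 |

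Five events in 800 subject-years would be 0.63 (0.20 to 1.46) per 100.

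**5. Precision when events repeat.** For 1200 events in 800 subject-years the rate is 150, with an exact Poisson interval of 141.6 to 158.7. If clustering within subjects raises the variance fourfold (assumed), 150 ± 1.96 × √(4 × 1200)/800 × 100 gives 133.0 to 167.0. A plain Poisson interval on E/100PY would then be too narrow.

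**The case against.** Much can be said for the plan as written.

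- **People are counted.** A reader might infer that the SAP has no person-based incidence. It does, in the overview, SOC/PT and subgroup tables. What is absent is a person-based rate that accounts for time at risk.
- **E/100PY is correct for its definition.** A reader might infer that the primary safety rate is inflated. No AE rate is designated primary. E/100PY exceeds a count of distinct illnesses only by an unknown amount, and the excess raises the reported burden, so it cannot hide harm.
- **A reader can work out a limit.** Event counts and years are shown with the rate, so a zero-event upper limit can be derived by hand. This stands for zero events. It fails once subjects have several events, because time to first event and within-subject clustering cannot be recovered from totals.
- **The study is descriptive.** This is true, but efficacy is descriptive too and has intervals.
- **Merging worsening records would be risky.** This stands. Protocol 5.3.1.1 carries ongoing parent-study AEs into this study's eCRF, and the new onset date is what makes their on-study worsening treatment-emergent. A merge could move the onset before the first dose and lose the event. It would also depart from Protocol 8.1.5, and the documents describe no field that links a worsened record to its predecessor.

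**Conclusion.** The gap is real but limited. E/100PY is the only exposure-adjusted AE measure and counts every record, worsenings included. The planned n (%) counts people but ignores unequal follow-up. Neither has an interval. The plan therefore yields no exposure-adjusted risk per subject and no stated precision for its primary objective. This is a worthwhile reporting improvement; the rate formula itself is not in error.

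The size of the worsening effect cannot be given, because the share of AEs that worsen is not in the documents. The precision figures (0.92, 0.46 and 0.31 per 100 subject-years for zero events) rest on 400 treated subjects and assumed mean exposures of 1, 2 and 3 years.

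**What to change.** In SAP 11.1:

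1. For each AE overview category, for SAEs and for each AE of special interest, add the number of subjects with a first event per 100 subject-years at risk, with time censored at the first event, and an exact Poisson 95% interval.
2. Give E/100PY a 95% interval that allows for repeat events within a subject, for example a subject-clustered variance.
3. State the clock for time at risk. SAP 9.0 defines two exposure totals, one from the first dose in this study and one from the first adalimumab dose in the parent study, and the rate paragraph does not say which applies.
4. Keep the raw E/100PY as defined and do not merge worsening records. At most, add a sensitivity count of distinct episodes that still treats on-study worsening of a pre-existing AE as treatment-emergent.

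The cost is a small amount of programming and some table space. AE collection does not change and no new data are needed.

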Subjects may be on only one of the allowed systemic immunosuppressants in addition to a systemic corticosteroid, at any timepoint.

Study visits will occur at Week 0, 2, 4, 8, 12, 18 and every 12 weeks thereafter. Efficacy assessments will be performed at every visit (Section 5.3.1). Both of the subject's eyes should be evaluated. **There will be no designated "study eye."**

Subjects who enter the study due to Treatment Failure in Study M10-877 or Study M10-880 and fail to achieve adequate control of their disease flare within the first 8 weeks may discontinue from the study.

Any other subject experiencing a uveitis flare during the study as determined by the investigator may discontinue from the study. Subjects may continue in the study, if it is determined by the investigator that the flare was triggered by a reduction or discontinuation in concomitant corticosteroid or systemic immunosuppressive therapy where further adjustment to the concomitant therapy may be warranted. Any subject continuing to have an active uveitis flare for 4 weeks or more should be discontinued from the study.

The site research staff will instruct and supervise subjects or a designee on proper injection technique at the scheduled visits. Subjects or a trained designee will administer adalimumab outside of clinic visits according to the specified dosing schedule.

An Independent Data Monitoring Committee (IDMC) will be established to independently monitor and assess data for Study M10-877, Study M10-880 and Study M11-327. The IDMC will be in effect until the end of both Study M10-877 and Study M10-880. At each committee meeting, the IDMC will undertake a comprehensive review and assessment of the cumulative safety data, which will include M11-327 study data.

Subjects may discontinue adalimumab treatment at any time during study participation. Subjects that end study participation early will have an Early Termination Visit. No study drug will be administered or injected at the final visit.

Safety data will be collected in the form of adverse events, physical examination, vital signs and laboratory tests throughout the treatment period and up to 70 days after the last injection in this study. All subjects will have a 70-day follow-up phone call or clinic visit to obtain follow-up information on any new or ongoing adverse events. The 70-day follow-up phone call will not be required for any subject that initiates commercial adalimumab after the end of study participation.

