If, during the course of study drug administration, the subject prematurely discontinues study drug use, the procedures outlined for the Final/Early Termination Visit must be completed within 2 weeks of the last dose of study drug, and preferably prior to the

initiation of another therapy. However, these procedures should not interfere with the initiation of any new treatments or therapeutic modalities that the Investigator feels are necessary to treat the subject's condition. Following discontinuation of the study drug, the subject will be treated in accordance with the Investigator's best clinical judgment.

All attempts must be made to determine the date of the last dose of study drug and the primary reason for premature discontinuation. The information will be recorded on the appropriate eCRF page. Subjects who prematurely discontinue will not be replaced.

A final phone call or clinic visit will be completed approximately 70 days after the last dose of study drug to determine the status of any ongoing adverse events/serious adverse events or the occurrence of any new adverse events/serious adverse events. The call/visit information should be documented in the subject's source documents per Appendix D, Day 70 Follow-up (Phone Call or Clinic Visit). The 70-day follow-up phone call or clinic visit will not be required for any subject that initiates adalimumab therapy not supplied in the context of the clinical trial after the end of study participation.

For subjects that are considered lost to follow-up, reasonable attempts must be made to obtain information on the final status of the subject. At a minimum, two phone calls must be made and one certified letter must be sent.

Following country and local (if applicable) regulatory approval and/or applicable local reimbursement approval of the study drug in a country, subjects should return to their next scheduled study visit as specified in the protocol. The termination visit should be conducted in place of their regular scheduled study visit. These subjects will be considered as having completed the study.

The entire study will be terminated in March 2018. Subjects who remain active in this clinical trial on 15 February 2018 should be contacted by the site to return for their study termination visit. Sites should complete the termination visit by 15 March 2018 for all of the remaining active subjects. These subjects will be considered as having completed the study.

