8.1.5 Analysis of Safety

Treatment-emergent AEs will be summarized using descriptive statistics.

Treatment-emergent AEs are defined as events with an onset date on or after the first study drug administration until 70 days following the last study drug administration. In case of increasing severity of an existing AE, the worsening will be considered as a new AE with a new onset date.

AEs will be tabulated by system organ class and preferred term whereby the most current implemented MedDRA dictionary will be used. Also, summaries by severity and relationship to study drug will be done. Certain AEs, like serious or severe, leading to premature withdrawal, will be listed and described in detail. AEs of special interest for treatment with biologics will be defined in the SAP and analyzed separately.

Other safety variables like laboratory data and vital signs will be described by descriptive statistics as mentioned before. In addition, shift tables and listings will be provided for abnormal values whereby the normal range of the analyzing laboratory will be used.

The IDMC will undertake a comprehensive review and assessment of the cumulative safety data until the completion of Study M10-877 and Study M10-880. Please refer to Section 5.5.5.1 for additional information regarding IDMC review.

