## Rx Day

- = Date of the measurement – Day 1 + 1 if date of measurement  $\geq$  Day 1 date, or
- = Date of the measurement – Day 1 if date of measurement  $<$  Day 1 date.

All time points and corresponding time windows for efficacy analyses are defined based on Rx Days for efficacy analyses. If more than one assessment is included in a time window the assessment closest to the nominal day should be used. If there were two observations equally distant to the nominal day, the latest one will be used in analyses. If more than one assessment is included on the same day, then the last assessment on that day will be used in analyses.

The following visit windows will be used for efficacy analyses:

Visit Windows			
Week	Nominal Rx Day	First Rx Day	Last Rx Day
0	1	-	1
2	15	2	22
4	29	23	43
8	57	44	71
12	85	72	106
18	127	107	169
$18+i*12^a$	$127+i*84$	$170+(i-1)*84$	$169+i*84$

a     i = 1, 2, 3, 4 etc.

Rx Days for safety analyses are calculated for each time point relative to the first adalimumab dose date in Study M10-877, M10-880 or M11-327. Rx days are negative values when the time point of interest is prior to the first adalimumab dose day. Rx days are positive values when the time point of interest is after the first adalimumab dose day. The day of the first dose of adalimumab is defined as Rx Day 1, while the day prior to the first adalimumab dose is defined as Rx Day –1 (there is no Rx Day 0).

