## **9.0 Study Drug Exposure and Compliance**

Exposure to adalimumab in days (d) will be defined as follows:

Treatment exposure (days)

- = date of last dose of adalimumab in Study M11-327
- date of first dose of adalimumab in Study M11-327
- + 14 (days)

In addition, the total amount of exposure from first adalimumab dose in Study M10-877/M10-880 will be calculated as follows:

Treatment exposure (days)

- = date of last dose of adalimumab in Study M11-327
- date of first dose of adalimumab in Study M10-877/M10-880 or Study M11-327
- + 14 (days)

Exposure will be presented in weeks.

Exposure will be summarized by number of subjects, mean, standard deviation, minimum, first quartile, median, third quartile and maximum in the safety set. In addition, exposure

will be categorized and counts will be given for the number of subjects in the respective interval.

Treatment compliance (%) is defined as the number of adalimumab injections received divided by the number of injections planned in Study M11-327. Tabulations for treatment compliance will display the number of observations, mean, standard deviation, minimum, median and maximum.

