### **Subgroup Analyses of Adverse Events**

Analyses of AEs per subgroup will be presented for the AE overview. The number and percentage of subjects experiencing AEs as well as E/100PYs will be tabulated overall.

Subgroups used for the analyses are:

- Concomitant use of corticosteroids (yes, no)
- Baseline immunosuppressant usage (yes, no)
- Baseline azathioprine usage
- Baseline cyclosporine usage
- Baseline methotrexate usage

- Baseline mycophenolate mofetil or an equivalent drug (e.g., mycophenolic acid) usage
- Baseline tacrolimus usage

An AE overview (with number and percentage of subjects experiencing treatment-emergent AEs as well as E/100PYs) will also be presented separately for

- treatment periods with/without concomitant use of corticosteroids
- treatment periods with corticosteroid dose  $> 0$  to  $\leq 15$  mg/day
- treatment periods with corticosteroid dose  $> 15$  mg/day
- treatment periods with/without concomitant use of immunosuppressant
- treatment periods
  - without concomitant use of corticosteroids and immunosuppressant
  - with concomitant use of corticosteroids only
  - with concomitant use of immunosuppressant only
  - with concomitant use of corticosteroids and immunosuppressant

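### The adverse event rate per 100 subject-years counts events to 70 days after the last dose but person-time only to 14 days, and the steroid and immunosuppressant period tables have no rule for events in between

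*SAP*

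**What the plan says.** **Numerator.** The rate in SAP 11.1 is a treatment-emergent rate, with repeat events counted. SAP 11.1 defines such events as starting on or after the first M11-327 dose and "no more than 70 days after the last dose of study drug administration". Protocol 8.1.5 sets the same limit: "until 70 days following the last study drug administration".

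**Denominator.** "The denominator of the rates will be the total number of days exposed to study drug summed across all treated subjects divided by 365.25". SAP 9.0 defines exposure as last M11-327 dose minus first M11-327 dose plus 14 days. A second formula follows: "In addition, the total amount of exposure from first adalimumab dose in Study M10-877/M10-880 will be calculated as follows". It starts earlier for subjects who received adalimumab in a parent study, but it also stops at last dose plus 14 days.

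**Where the rate is used.** SAP 11.1 plans it for the event overview, for all events and serious events by system organ class and preferred term, for the subject-level subgroups, and for "treatment periods with/without concomitant use of corticosteroids", with further splits by steroid dose and immunosuppressant use.

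**Medication status after the last dose.** SAP 7.5 does not treat a drug started after the last adalimumab dose as concomitant. Protocol Table 1 marks adverse event monitoring at the 70-day follow-up, but no concomitant medication check.

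**The concern.** A rate per unit of person-time needs events and time drawn from the same window. Here the event window is 56 days longer per subject, and no section reconciles the two. Long-term safety is the primary objective (SAP 4.1), and this is the plan's exposure-adjusted measure of it.

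The period tables raise a further problem. An event on day 40 after the last dose is treatment-emergent, but the SAP does not say which steroid or immunosuppressant period it belongs to, or whether it belongs to any. Two programmers could follow the text and produce different contrasts between periods.

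**Working it through.** The documents state no adverse event rate or person-years total, so there is no figure of the plan's own to reproduce.

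**Step 1: the gap.** Events run to day 70 and person-time to day 14, so the gap is 70 − 14 = 56 days per subject under either exposure formula. For the roughly 400 subjects expected (Protocol 5.2) the ceiling is 400 × 56 / 365.25 = 61.3 subject-years.

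**Step 2: overall rate.** Let D be mean M11-327 exposure in days and f the mean share of the 56-day tail in which events are observed. With a constant event rate, events accrue over D + 56f days and are divided by D days, so the overstatement is 56f/D. Neither D nor f is in the documents; both are assumed below. D is the time from first to last dose plus 14 days.

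| First to last dose | D (days) | f = 0.2 | f = 0.5 | f = 1 |
|---|---|---|---|---|
| 1 year | 379.25 | 3.0% | 7.4% | 14.8% |
| 2.5 years | 927.1 | 1.2% | 3.0% | 6.0% |
| 4 years | 1475 | 0.8% | 1.9% | 3.8% |

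Example: 2.5 × 365.25 + 14 = 927.1, and 56 × 0.2 / 927.1 = 1.2%. For a group with only 12 weeks of exposure (84 days), the ceiling is 56/84 = 67%.

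**Step 3: what bears on f.**
- After premature discontinuation, the "Final/Early Termination Visit must be completed within 2 weeks of the last dose of study drug". No drug is given at the final visit (Protocol 5.1). Events in the tail are therefore learned of mainly through the 70-day contact.
- That contact is waived for some: "The 70-day follow-up phone call will not be required for any subject that initiates commercial adalimumab after the end of study participation". Protocol 6.1.4 sends new events in such subjects to post-marketing reporting. For them f is near 0.
- SAP 8.0 foresees subjects still ongoing at an interim analysis. They have no tail, so f = 0.
- Protocol 6.1.4 allows 70-day contacts after database lock. Serious events and events of special interest must then be captured; others are only considered for inclusion.

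Thus f may be low, and f = 1 is an upper bound.

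**Step 4: period tables.** Let one medication class hold a share s of exposure (assumed 0.5 to 0.2). If every tail event goes to that class, its rate rises by 56f/(sD) and the other class does not move. At 2.5 years:

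| s | sD (days) | f = 0.2 | f = 0.5 | f = 1 |
|---|---|---|---|---|
| 0.5 | 463.6 | 2.4% | 6.0% | 12.1% |
| 0.2 | 185.4 | 6.0% | 15.1% | 30.2% |

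If tail events split in proportion to time, both classes rise by the same 56f/D and the contrast is unbiased. If tail events are left out, neither class changes.

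**The case against.** The best defence is that the effect is small, cautious and disclosed. The study is descriptive with a single arm, the error raises an adverse event rate, the heading says exposure is the basis, and years of exposure are printed beside each rate. Overall counts, percentages and listings are unaffected. With many subjects moving to commercial drug, f could be about 0.2 and the overall overstatement near 1%. All of this stands for the overall rate at multi-year exposure. It does not remove the mismatch, and it answers neither short-exposure groups nor the period tables.

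On the period tables, it can be said that the term treatment periods and the concomitant medication definition in SAP 7.5 both lean toward on-treatment time. They do, but neither says what to do with an event on days 15–70. The 12–30% range is a worst case that needs a fully observed tail and all its events in one class.

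Two stronger readings are tempting, and the documents do not support them:

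- *The denominator is undefined, so the bias could run in either direction.* A reader might infer this from the second formula in SAP 9.0 and from safety Rx Days, which count "relative to the first adalimumab dose date in Study M10-877, M10-880 or M11-327". But SAP 11.1 does name days exposed to study drug, the first formula in SAP 9.0 is M11-327 only, and events start at the first M11-327 dose. The parent-inclusive total is introduced as an addition, and Rx Days place time points rather than measure exposure. M11-327 exposure is the natural reading, and a cross-reference would settle it.
- *Medication status is known through the tail, because recording runs to the end of the study.* The end of study in Protocol 13.0 is a trial-level date tied to the last subject. It does not fix when an individual's medication recording stops.

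**Conclusion.** The mismatch is explicit in the SAP and should be corrected. The overall rate is biased upward, modestly at multi-year exposure and more where exposure is short. These sizes rest on a constant event rate through the tail and on assumed D and f; a lower rate after stopping would shrink them and a higher one would enlarge them. The missing assignment rule in the period tables is the more consequential part, because it can create or hide a difference between periods. How much it does so cannot be determined from the documents, and a proportional split gives no distortion. The 56-day gap is certain; its numerical effect is not.

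**What to change.** **(a) Cross-reference.** In the rate subsection of SAP 11.1, cite the M11-327 exposure formula in SAP 9.0. This is clarification only.

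**(b) Overall, SOC/PT and subject-level subgroup rates.** Match the windows in one of two ways:
- keep the 70-day event window and run person-time to the earliest of last dose plus 70 days, the last adverse event contact whose events are in the locked database, or the data cutoff, with events counted to the same date and the denominator labelled subject-years of observation; or
- cut both events and person-time at last dose plus 14 days.

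The locked-database condition matters. Crediting full person-time for a contact made after lock, when non-serious events may not be entered, would understate the rate.

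**(c) Treatment-period tables.** Limit both events and person-time to the first M11-327 dose through last dose plus 14 days, and assign each event to the period in force at its onset date. Add a footnote that later events appear only in the overall n (%) tables and listings.

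**Cost.** SAP wording, one derived end date and one onset-date cut. The rates will not match earlier summaries made under the present rule, and the period tables will hold fewer events than the overall tables. The protocol's 70-day treatment-emergent definition stays as it is for the overall counts and percentages.
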